7.5.3 Drug Concentration Measurements and Bioassays

To assess the UX007 metabolites, blood samples will be collected approximately 90 minutes following consumption of food and study drug at the Baseline Visit and at 6-month intervals throughout the Treatment Extension Period (or Early Termination). For each sample collection, the time elapsed since last study drug administration will be recorded on the CRF. The following UX007 metabolites will be assessed:

- C4 ketone: beta-hydroxybutyrate (BHB)
- C5 ketones: beta-hydroxypentanoate (BHP)
- Heptanoate

7.5.4 Safety Measures & General Assessments

General assessments include medical history and demographics. Safety will be evaluated by the incidence, frequency, severity, and relatedness of AEs and SAEs, including clinically significant changes from baseline to scheduled time points in vital signs, weight, physical examination, and clinical laboratory evaluations. Pregnancy testing (or pregnancy of partner), suicidal ideation and behavior assessments, and concomitant medications will also be monitored. Refer to the Study Reference Manual for additional details.

7.5.4.1 Medical History and Triheptanoin Treatment History

Medical history will be obtained at the Baseline Visit for all subjects not previously enrolled in UX007G-CL201. General medical information includes subject demographics (date of birth, ethnicity, and sex) and a history of major medical illnesses, diagnoses, and surgeries. The review will also include an assessment of phenotypic characteristics associated with Glut1 DS, including seizures, cognitive impairment, movement disorders, and microcephaly. The specific history of Glut1 DS will be recorded, along with date of onset, clinical presentation, and date and method of confirmed diagnosis. Any available family history of Glut1 DS will be noted including diagnosis, disease course, treatment and outcome.

Glut1 DS maintenance treatment history, including UX007 (triheptanoin) treatment history, and relevant concomitant medications will be recorded (start date, stop date, dose, dose regimen). Treatments include prescribed diets, other standard of care treatments, and all other relevant concomitant medications (e.g. seizure medications, L-carnitine, vitamin supplements, etc.). Medications include prescription, over-the-counter, herbal and nutritional supplements. Any relevant concomitant therapy, including physical/occupational therapy will be recorded.

7.5.4.2 Vital Signs and Weight

Vital signs will include seated systolic blood pressure and diastolic blood pressure measured in millimeters of mercury (mm Hg), heart rate in beats per minute, respiration rate in breaths per minute, and temperature in degrees Celsius (°C). Vital signs measurements will be

performed at every clinic visit before any additional assessments are completed. At each visit, weight (in kilograms) will be obtained using a scale. Clinically significant changes will be recorded as AEs.

7.5.4.3 Physical Examination

Complete physical examinations will be performed at the Baseline Visit and at 6-month intervals for the duration of the study (or Early Termination Visit). Physical examinations will include assessments of general appearance; head, eyes, ears, nose, and throat; the cardiovascular, dermatologic, lymphatic, respiratory, gastrointestinal, musculoskeletal, and neurologic systems. Clinically significant changes will be recorded as AEs.

7.5.4.4 Clinical Laboratory Tests

The clinical laboratory evaluations to be performed in this study include routine serum chemistry, hematology, and urinalysis; specific analytes are listed in [Table 7.5.4.4.1](#). Clinical laboratory testing will be performed at each scheduled study clinic visit (or Early Termination visit). Blood and urine samples will be collected; fasting is not required. Refer to the Study Reference Manual for additional details.

Table 7.5.4.4.1: Clinical Laboratory Assessments

Chemistry	Hematology	Urinalysis
Alanine aminotransferase (ALT)	Hematocrit	Appearance
Alkaline phosphatase	Hemoglobin	Color
Aspartate aminotransferase (AST)	Platelet count	pH
Bilirubin (total)	Red blood cell (RBC) count	Specific gravity
Blood urea nitrogen (BUN)	White blood cell (WBC) count	Ketones
Calcium		Protein
Chloride		Glucose
Serum creatinine		
Gamma-glutamyl transpeptidase (GGT)		Pregnancy test (if applicable)
Serum glucose		
Potassium		
Protein (albumin and total)		
Sodium		

Subjects who experience a SAE possibly, probably, or definitely related to study drug or other AE of concern may, at the discretion of the investigator (and/or medical monitor), have additional blood or urine samples taken for safety laboratory tests.

7.5.4.5 Pregnancy Testing

Female subjects of childbearing potential will have urine pregnancy tests at each scheduled study visit (or Early Termination). Females considered not of childbearing potential include those who have not experienced menarche, are post-menopausal (defined as having no menses for at least 12 months without an alternative medical cause); or are permanently sterile due to total hysterectomy, bilateral salpingectomy, or bilateral oophorectomy.

Female subjects with a positive pregnancy test at the Baseline visit will not be enrolled in the study. Pregnancy in subject or partner must be reported (Section 8.5.5.1); pregnant subjects will be discontinued from the study. Additional pregnancy tests may be performed at any time in which pregnancy status is in question. A serum pregnancy test will be performed in the event of a positive or equivocal urine pregnancy test result, or can be performed if pregnancy test by urine is not feasible.

Experience with UX007 (triheptanoin) in pregnant women is limited. The study drug may involve risks to a pregnant female or unborn baby which are currently unknown. Sexually active fertile males or females of childbearing potential must use highly effective contraception as determined by the investigator during heterosexual intercourse throughout the study period and for 30 days after stopping the study drug. Examples of some highly effective methods (CTFG 2014) include:

- Combined (estrogen and progestogen containing) hormonal contraception associated with inhibition of ovulation
- Progestogen-only hormonal contraception associated with inhibition of ovulation
- Intrauterine device (IUD)
- Intrauterine hormone-releasing system (IUS)
- Bilateral tubal occlusion
- Vasectomized partner
- Sexual abstinence (i.e., refraining from heterosexual intercourse during the entire period of risk associated with the study treatments, when this is in line with the preferred and usual lifestyle of the subject)

7.5.4.6 Suicidal Ideation and Behavior Assessments

Assessment of suicidal ideation and behavior is a regular part of development programs involving AEDs and other neurologic drugs with central nervous system activity (FDA Draft Guidance 2012). The Columbia Suicide Severity Rating Scale (C-SSRS) is a standardized suicidal rating instrument used to assess the suicidal ideation and behavior in an at-risk population (Posner et al. 2011). To prospectively assess suicidal ideation and behavior, the C-SSRS will be administered by a clinician. Depending on the cognitive state of the subject, some questions within the C-SSRS may be deemed by the investigator to be inappropriate to ask the subject and can be omitted. Suicidal ideation and behavior will be

assessed in subjects ≥ 10 years of age at each visit. The Baseline questionnaire will be administered on the initial visit; the Since Last Visit questionnaire will be administered at all subsequent visits. The responses to the questionnaire will be reviewed by site personnel during the study visit; if emergent suicidal ideation or behavior is indicated, the investigator should promptly evaluate the subject to ensure proper management and protection of subject safety. Determination of whether the subject should continue on study will be made by the investigator based on the severity of symptoms and follow-up needed, and the Sponsor will be informed.

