¹⁰ The Columbia Suicide Severity Rating Scale (C-SSRS) baseline questionnaire will be administered on the initial visit; the Since Last Visit questionnaire will be administered at all subsequent visits.

¹¹ At the Baseline visit, an interview with the study dietitian will establish daily caloric intake and UX007 dose. Subjects and/or caregivers are required to maintain a record of the subject's daily diet in a diary for the 3 days prior to each subsequent visit. The diet diary will be reviewed by study personnel at each visit to the clinic. The dietitian may telephone subjects and/or caregivers, as needed, to provide dietary advice and support.

¹² A subject may have been off UX007 treatment prior to enrollment; in these cases, UX007 may be titrated per discretion of the investigator. Study drug may be dispensed at Visits 6, 8, 10, and 12 to subjects who make optional study site visits to attain study drug as needed at the request of the Investigator.

¹³ Refer to Pharmacy Manual for instructions on return of empty and opened study drug bottles. Phone calls at Visits 6, 8, 10, and 12 will inquire about study drug consumption and remaining supply; in lieu of a phone call, subjects may also visit the study site at the study site's discretion.

¹⁴ Safety Follow-up Phone Call to be conducted 30-35 days after last dose of study drug. The last subject's Safety Follow-up Phone Call is the End-of-study Time Point. The site personnel will initiate this safety follow-up telephone call to collect information on any ongoing or new AEs, serious adverse events (SAEs), and concomitant medications. Appropriate follow-up should continue until all safety concerns, in the Investigator's opinion, are resolved.

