7 INVESTIGATIONAL PLAN

7.1 Overall Study Design and Plan

UX007G-CL202 is an open-label, single-arm, multicenter extension study to assess the long-term safety and efficacy of UX007 in Glut1 DS. The study will enroll up to 40 pediatric, adolescent, and adult Glut1 DS subjects who have completed the UX007G-CL201 study and, at the discretion of the Sponsor, additional subjects from participated in other clinical studies, ISTs, or expanded access/compassionate use treatment programs. Figure 7.1.1 provides a schematic of the study design.

Figure 7.1.1: UX007G-CL202 Study Schema

For continuing UX007G-CL201 subjects, the Week 52 visit of that study may be conducted in conjunction with the Baseline visit for this study to avoid duplication of assessments. Following the Baseline visit, subjects will return to the study site at 3-month intervals from Baseline during Year 1 of the Treatment Extension, and 6-month intervals from Baseline during Years 2 and 3. Phone calls will take place 3-months between scheduled study site visits during Years 2 and 3 to collect adverse events and concomitant medications updates and to inquire about study drug consumption and remaining supply; in lieu of the phone call, subjects may also visit the clinic at the study site's discretion. Additionally, optional study site visits may occur 3-months between scheduled study site visits during Years 2 and 3 to allow subjects to attain study drug as needed at the request of the Investigator. A Safety Follow-up Phone Call will be conducted 30-35 days after last dose of study drug. The last subject's Safety Follow-up Phone Call is the End-of-study Time Point. Subjects will record seizure occurrence in a diary throughout the study; diet diaries will also be completed by the subject for the 3 days preceding each scheduled visit after Baseline. Overnight electroencephalograms (EEG) will be conducted in all subjects to monitor absence seizures. Safety assessments and a clinical neurological evaluation will further enable the characterization of long-term safety and maintenance of effect. Metabolites of UX007 in the blood will also be assayed.

UX007 dosing will be targeted at 35% of total daily caloric intake throughout the study. Subjects receiving a different dose of UX007 at study entry may continue treatment at the

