7.3.1 Inclusion Criteria

Individuals eligible to participate in this study must meet all of the following criteria:

- 1) Diagnosis of Glut1 DS by cerebrospinal fluid glucose concentration, erythrocyte 3-O-methyl-D-glucose uptake assay, or *SLC2A1* molecular genetic testing. Information will be obtained from medical records.
- 2) Males and females, aged at least 1 year at the time of informed consent
- 3) Completion of UX007G-CL201 study (NCT01993186). Glut1 DS patients who received UX007/triheptanoin treatment as part of other clinical studies, ISTs, or

expanded access/compassionate use treatment programs may be eligible at the discretion of the sponsor.

- 4) Provide written informed consent or verbal assent (if possible) with written informed consent by a legally authorized representative after the nature of the study has been explained, and prior to any research-related procedures
- 5) Must, in the opinion of the investigator, be willing and able to complete all aspects of the study, and comply with accurate completion of the seizures diary
- 6) Females of childbearing potential must have a negative urine pregnancy test at Baseline and be willing to have additional pregnancy tests during the study. Females considered not of childbearing potential include those who have not experienced menarche, are post-menopausal (defined as having no menses for at least 12 months without an alternative medical cause), or are permanently sterile due to total hysterectomy, bilateral salpingectomy, or bilateral oophorectomy.
- 7) Participants of child-bearing potential or fertile males with partners of child-bearing potential who are sexually active must consent to use a highly-effective method of contraception as determined by the investigator from the period following the signing of the informed consent through 30 days after last dose of study drug.

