7.3.2 Exclusion Criteria

Individuals who meet any of the following exclusion criteria will not be eligible to participate in the study:

- 1) Any known hypersensitivity to triheptanoin that, in the judgment of the investigator, places the subject at increased risk for adverse effects
- 2) History of, or current suicidal ideation, behavior and/or attempts
- 3) Pregnant and/or breastfeeding an infant
- 4) Unwilling or unable to discontinue use of a prohibited medication (barbiturates, pancreatic lipase inhibitors) or other substance that may confound study objectives. Use of up to 3 concomitant AEDs is allowed, provided dose has been stable at least 14 days prior to Baseline.
- 5) Use of any investigational product, drug or supplement (other than UX007) within 30 days prior to Baseline, or at any time during the study
- 6) Has a condition of such severity and acuity, in the opinion of the investigator, that it warrants immediate surgical intervention or other treatment
- 7) Has a concurrent disease or condition, or laboratory abnormality that, in the view of the investigator, places the subject at high risk of poor treatment compliance or of not completing the study, or would interfere with study participation or introduce additional safety concerns (e.g. other concurrent neurological or psychiatric disorders).

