7.4.4.1 Study Duration

The planned duration of treatment in this study is 3 years, or until one of the following occurs: the subject withdraws consent, the subject is discontinued from the study at the discretion of the Investigator or Ultragenyx, the study is terminated, or until commercial availability of study drug in a subject's region, whichever occurs first. The length of the study is intended to define whether UX007 is safe for long-term use and provide sufficient insight on sustained clinical effects. A Safety Follow-up Phone Call will be conducted 30-35 days after last dose of study drug. The last subject's Safety Follow-up Phone Call is the End-of-study Time Point.

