8.9.5 Suicidal Ideation and Behavior

The number and percentage of subjects with suicidal ideation or suicidal behavior will be presented at study baseline and post-baseline by category. If more than one suicidal ideation or suicidal behavior was reported for the same period/visit, the one with greatest severity will be used for the same visit in the summary.

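### As worded, a child who turns 10 during the study starts on the Since Last Visit C-SSRS and has no structured C-SSRS baseline in this study

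*Protocol*

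**What the plan says.** Protocol 7.5.4.6 states two rules. The first sets eligibility by age: suicidal ideation and behavior are "assessed in subjects ≥ 10 years of age at each visit". The second sets the form by visit: "The Baseline questionnaire will be administered on the initial visit; the Since Last Visit questionnaire will be administered at all subsequent visits". Footnote 10 of the schedule of events (Protocol Table 2.1) repeats the second rule without the age condition: "baseline questionnaire will be administered on the initial visit; the Since Last Visit questionnaire will be administered at all subsequent visits". Footnote 10 of SAP Appendix B does the same.

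Three other provisions matter:

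- Subjects may enter if "aged at least 1 year at the time of informed consent" (Protocol 7.3.1).
- On length of treatment, Protocol 7.4.4.1 says: "The planned duration of treatment in this study is 3 years". It also lists events that can end treatment sooner.
- Clinic visits are at "3-month intervals from Baseline during Year 1 of the Treatment Extension, and 6-month intervals from Baseline during Years 2 and 3" (Protocol 7.1). Table 2.1 marks the C-SSRS at each of these visits and at none of the phone contacts.

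On analysis, SAP 8.9.5 says only that the number and percentage of subjects with ideation or behavior "will be presented at study baseline and post-baseline by category".

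**The concern.** The two rules run on different clocks. Eligibility can begin at any clinic visit, but the Baseline form exists only at the first one. A child who is 9 at Visit 1 is too young for the scale that day, and once old enough is past the only visit at which the Baseline form is given.

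Protocol 7.5.5 includes this assessment because the disease affects the central nervous system and most subjects are expected to take an AED. Protocol 7.5.4.6 asks the investigator to act when emergent ideation or behavior appears. For a child who starts on the Since Last Visit form, neither the investigator nor the analysis has a C-SSRS starting point from this study to compare with. In the SAP table, such children join the post-baseline row without having been in the baseline row, so the two rows describe different sets of subjects and no rule says so.

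**Working it through.** The plan gives no figure to reproduce. The check sets the rules side by side and then does arithmetic on the visit grid.

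**1. Who can be affected.** The threshold is 10 years and planned treatment is 3 years. The lowest entry age that reaches 10 on study is 10 − 3 = 7. Children aged about 7 to under 10 at entry can therefore cross the threshold. The documents give no age distribution, so the number is unknown.

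**2. Which form they get.** Take a child under 10 at Visit 1.

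- At Visit 1 the age rule means no C-SSRS, so no Baseline form.
- At the first clinic visit at age 10 or older the age rule applies. That visit is not the initial one, so the form rule gives Since Last Visit.
- No text in Protocol 7.5.4.6, footnote 10 of either schedule, or SAP 8.9.5 makes an exception.

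**3. How far back the first form reaches.** The documents do not describe the contents of the two forms. I take the Since Last Visit form, from its name, to reach back to the preceding scheduled clinic visit, and the Baseline form to be the one that records earlier history. Clinic visits fall at Months 0, 3, 6, 9, 12, 18, 24, 30 and 36. On-study time before the look-back equals the month of the preceding clinic visit.

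| First C-SSRS at Month | Look-back starts at Month | Look-back (months) | On-study months before the look-back |
|---|---|---|---|
| 3 | 0 | 3 | 0 |
| 6 | 3 | 3 | 3 |
| 9 | 6 | 3 | 6 |
| 12 | 9 | 3 | 9 |
| 18 | 12 | 6 | 12 |
| 24 | 18 | 6 | 18 |
| 30 | 24 | 6 | 24 |
| 36 | 30 | 6 | 30 |

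The range is 0 to 30 months. In every row, if all scheduled visits are attended, the tenth birthday falls after the preceding clinic visit, so all time at age 10 or older is covered. The uncovered months lie wholly below the age threshold.

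**4. What the SAP does with them.** SAP 5.3 takes the baseline of Non-Rollover subjects from assessments on or before Month 0, so such a child has no C-SSRS baseline. For Rollover subjects it takes the UX007G-CL201 baseline. These documents do not say whether that study used the scale, or from what age. SAP 8.9.5 has no rule for a subject whose baseline is missing.

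**5. Comparison with another instrument.** Protocol 7.5.2.3.1 fixes age at informed consent for the SF-10 and SF-12v2 and then states what happens when a subject turns 18. The C-SSRS text attaches age to each visit and states no transition rule.

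**The case against.** The strongest case is that this is a narrow drafting gap with real backstops. Much of it stands, and it rules out several stronger readings that a reader might infer.

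- **That suicidality in these children is never captured.** The documents do not support this. Exclusion criterion 2 bars anyone with "History of, or current suicidal ideation, behavior and/or attempts", with no age limit. Under Protocol 7.5.4.8, AEs are asked about at every visit and phone call, and clinically significant changes in ideation or behavior are recorded as AEs or SAEs at any age. These backstops are partial: no instrument is named for screening children under 10, and a general AE question is not a structured scale.
- **That the late form is the child's first C-SSRS ever.** This can be said only for the present study, because the procedures of UX007G-CL201 are not in the documents.
- **That an existing problem would be reported as emergent.** A known earlier problem makes the child ineligible. One that begins after the first dose in this study is treatment-emergent under SAP 8.9.1 in any case. SAP 8.9.5 defines no emergent category and no shift table for the scale.
- **That up to 2.5 years go unmonitored because of the form.** Thirty months is the extreme of the range. Prospective use of the scale in that time is withheld by the age threshold, as it is for younger children. The form rule removes only the later look back over it.
- **That one third of children under 10 are affected.** That figure, (10 − 7)/(10 − 1) = 3/9, needs an even spread of entry ages, for which the documents give no basis.

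The wording also allows other readings. If the initial visit means the subject's first C-SSRS visit, there is no gap, but the text does not say so and the footnotes point the other way. If age is fixed at entry, children who turn 10 are never assessed at all. The Study Reference Manual, which Protocol 7.5.4 cites for detail, may settle the matter, but it is not among these documents.

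**Conclusion.** The point holds in limited form. On the plain wording, a child under 10 at Visit 1 who turns 10 on study receives a Since Last Visit form as the first C-SSRS in this study, and has no structured C-SSRS baseline or history record here. SAP 8.9.5 then counts that child post-baseline with no baseline.

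The loss is the baseline record itself and its look-back before the preceding clinic visit: 0 to 30 on-study months, all below the age at which the protocol uses the scale. The group is children aged about 7 to under 10 at entry who stay long enough; its size is not given, and early ending of treatment would reduce it.

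This rests on three assumptions: that the initial visit means Visit 1, that age is judged at each visit, and that the Since Last Visit form reaches back to the preceding scheduled clinic visit. The conclusion does not depend on how many children are affected, and the same clarifying sentence is needed under the other readings.

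**What to change.** In Protocol 7.5.4.6, and in footnote 10 of both Protocol Table 2.1 and SAP Appendix B, tie the form to the subject instead of the study visit. Suggested text: *The Baseline questionnaire is used at the subject's first C-SSRS assessment, that is, the first scheduled clinic visit at age 10 or older; the Since Last Visit questionnaire is used from then on.*

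In SAP 8.9.5, do one of two things:

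- Take that first assessment as the subject's C-SSRS baseline. This needs a stated exception to SAP 5.3 and a note that the baseline was taken on treatment in this study, because anything reported on that form would otherwise leave the post-baseline count unnoticed.
- Keep the present table and identify subjects first assessed after Month 0 by footnote or listing. For what may be very few children, this is enough.

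The cost is one sentence in each place and a small change to the CRF form trigger. No visit, staff or instrument is added: the same clinician gives a different version of the same scale at a visit already scheduled.
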